7.3 Analysis of Safety Data for Objectives

7.3.1 Local Tolerability

Signs and symptoms of local tolerability pruritus, erythema, exudation, excoriation, lichenification as well as pain, burning, or stinging) will be summarized with changes from baseline.

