4.2.2 Secondary Endpoints

In the *S. aureus* MITT population, comparison of sites treated with DBI-001 or Aqueous Gel on the following microbial metrics:

- Change from baseline in abundance of *S. aureus* based on molecular diagnostic qPCR and CFU counts on samples obtained from treatment sites at days 7, 14, 21, 28, 35, and 42.
- Abundance of based on qPCR and CFU counts.
- Changes in the abundance and diversity of the microbiome as determined by 16s and/or whole genome sequencing.
- The proportion of subjects with a greater decrease in ADSI for the DBI-001-treated site than the Aqueous Gel-treated site.
- Change from baseline in signs and symptoms of local tolerability (pruritus, erythema, exudation, excoriation, and lichenification as well as pain, burning, or stinging) for the DBI-001-treated lesion and the Aqueous Gel-treated lesion.

INVESTIGATIONAL PRODUCT (IP)

Investigational Product and Aqueous Gel (Test Articles)

Test articles	Doses per Subject
1mL vial contains DBI-001 Gel with 10 ⁷ -10 ⁹ CFU / mL of	27 doses (once daily for 4 weeks)

ELIGIBILTY CRITERIA

Inclusion Criteria

Subjects must meet all of the following criteria to be included in the study:

1. Ability to understand, agree to, and sign the study Informed Consent. If the subject is unable to provide consent for him/herself, the subject's legally authorized representative may provide written consent.

2. A signed Health Information Portability and Accountability Act (HIPAA) authorization form which permits the use and disclosure of subject's individually identifiable health information.

3. Male or Female Subjects of any race 12-65 years of age.

4. Physician diagnosed clinically stable AD according to the criteria of Hanifin and Rajka with comparable anatomically symmetrical, bilateral target lesions (Hanifin and Rajka 1980). Each lesion must have an Atopic Dermatitis Severity Index (ADSI) score of ≥ 6 . It will be in the

opinion of the Investigator based on subject's medical history whether the lesions are clinically stable.

5. Female subjects of child-bearing potential must use at least one method of birth control that results in a low failure rate (i.e., less than 3 % per year) when used consistently and correctly such as implants, injectables, combined oral contraceptives, some intrauterine devices (IUDs), sexual abstinence or vasectomized partner for the duration of study participation.

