6.6.1 Grading of signs and symptoms of AD using ADSI

Both targeted treatment areas will be evaluated using the ADSI. The ADSI score represents the sum of the individual severity scores on none, mild, moderate, or severe for the following component signs and symptoms: erythema, pruritus, exudation, excoriation and lichenification. The investigators will only be required to calculate the ADSI at the Screening and Baseline visits to confirm that the subjects meet the inclusion criteria for disease severity. The ADSI for subsequent visits will be calculated during data analysis. The same observer-blinded investigator should perform the ADSI grading for each subject for the duration of a subject's participation in the study.

The same signs and symptoms of AD are also commonly use to evaluate application site reactions to topical product and serves a secondary role in characterizing tolerability. The sponsor will consider improvement in the ADSI and the individual signs and symptoms of AD an indicator of either a favorable therapeutic effect or the demonstration of the natural variation of AD over time. If the signs and symptoms increase in severity, the sponsor will consider this an indication of an application site reaction and/or the natural variation in AD over time. To further characterize local tolerability, subject self-reporting of pain, burning, or stinging will also be recorded. Each component is measured using the following scale:

Erythema score: (redness presents specifically in the target lesion)

0=none	No redness
1=mild	Mildly detectable erythema; pink
2=moderate	Dull red; clearly distinguishable
3=severe	Deep, dark red; marked and extensive

Exudation score: (oozing or crusting of the target lesion)

0=none	No oozing or crusting
1=mild	Minor or faint signs of oozing
2=moderate	Definite oozing or crusting present
3=severe	Marked and extensive oozing or crusting present

Excoriation score: (evidence of scratching in the target lesion)

0=none	No evidence of excoriation
1=mild	Slight excoriation present

2=moderate	Definite excoriation present
3=severe	Marked, deep, or extensive excoriation present

Pruritus: as reported by the subject as being the greatest intensity they have experienced within the last 24 hours at Baseline or since the last visit at subsequent visits.

0	None	No pruritus
1	Mild	Slight pruritus, not really bothersome
2	Moderate	Definite pruritus that is somewhat bothersome

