6.6.2 Local Tolerability

Tolerability will be evaluated based on calculating the scores for pruritus, erythema, exudation, excoriation, lichenification and the additional symptoms of pain, burning, or stinging using the following scale:

Pain, Burning, or Stinging: as reported by the subject as being the greatest intensity they have experienced within the last 24 hours at Baseline or since the last visit at subsequent visits.

0	None	No pain, burning, or stinging
1	Mild	Slight pain, burning or stinging sensation; not really bothersome
2	Moderate	Definite pain, burning or stinging that is somewhat
		bothersome
3	Severe	Significant pain, burning, or stinging sensation that causes definite
		discomfort and may interrupt daily activities and/or sleep.

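### Tolerability is planned only as change from baseline, largely on ADSI items, so average change can mask local reactions in a minority of subjects, and no within-subject count of worsening is planned.

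*Combined protocol and SAP*

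**What the plan says.** Section 7.3.1 is a single sentence. It lists the five signs and symptoms of AD and says that these "as well as pain, burning, or stinging) will be summarized with changes from baseline". It names no count of subjects who worsen, no shift table, no worst post-baseline score and no comparison between sides.

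The overlap with efficacy is explicit. In section 6.6.1 the ADSI sums severity scores "for the following component signs and symptoms: erythema, pruritus, exudation, excoriation and lichenification". Section 6.6.2 ends its list of tolerability items with "excoriation, lichenification and the additional symptoms of pain, burning, or stinging using the following scale". So five of the six tolerability items are the ADSI components, and the sixth lies outside the ADSI. Section 6.6.1 acknowledges that the shared set "serves a secondary role in characterizing tolerability". It reads a fall as a therapeutic effect or natural variation. For a rise, "the sponsor will consider this an indication of an application site reaction and/or the natural variation in AD over time".

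Section 4.2.2 makes change in these items a secondary endpoint "for the DBI-001-treated lesion and the Aqueous Gel-treated lesion". The Synopsis words both the objective and the endpoint as DBI-001 versus Aqueous Gel.

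On Day 1, section 6.5.2 places the AD assessment before application (step 4) and the tolerability assessment 30 minutes after it (step 11). Table 1, footnote c, gives the same timing. No pre-application score for pain, burning or stinging is stated.

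**The concern.** If a rise may be a reaction and a fall may be benefit, the two answer different questions, and an average of them answers neither. A product that helps most sites and irritates a few can show a favourable average change on an item while a material minority worsens on it. Worsening of AD is the first risk named under Potential Risks for this live bacterial product.

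The design offers a good control, because each subject carries a gel-treated site. Yet 7.3.1 does not use it to ask how many subjects worsened on the DBI-001 side and not on the gel side.

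Baseline adds a second problem. If the 30-minute score serves as baseline, stinging or redness provoked by the first dose becomes part of the reference value.

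**Working it through.** The plan gives no figure to reproduce: the sample size rests on clinical judgement (section 7.5), and no reaction rate is stated. The inputs from the documents are about 20 subjects, one site per treatment in each, and items graded 0 to 3. All rates below are assumptions.

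**1. Netting within one item.** Let r of 20 sites rise by 1 grade, q fall by 1 and the rest stay unchanged. Mean change = (r - q)/20.

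| Worse (r) | Better (q) | Mean | Median | Maximum | Worsened |
|---|---|---|---|---|---|
| 2 | 8 | -0.30 | 0 | +1 | 10% |
| 4 | 4 | 0.00 | 0 | +1 | 20% |
| 4 | 8 | -0.20 | 0 | +1 | 20% |
| 4 | 12 | -0.40 | -1 | +1 | 20% |
| 6 | 4 | +0.10 | 0 | +1 | 30% |
| 6 | 12 | -0.30 | -1 | +1 | 30% |

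The first and last rows share a mean of -0.30 with 10% and 30% worsened. The mean is positive only when r exceeds q. A sharper case is 4 sites at +2 and 16 at -1: mean (8 - 16)/20 = -0.40, median -1, with 20% worse by two grades.

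**2. What the maximum adds.** P(at least one of 20 worsens) = 1 - (1 - p)^20. This is 64%, 88%, 99% and above 99% for p = 5%, 10%, 20% and 30%. A maximum of +1 shows that someone worsened, but not how many.

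**3. What the component sign test adds (section 7.2.3).** Take the sharper case with gel sites unchanged: 16 pairs favour DBI-001 and 4 favour gel. Exact two-sided p = 2 x (1 + 20 + 190 + 1140 + 4845)/2^20 = 12392/1048576 = 0.012, in favour of DBI-001. The test nets in the same way.

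**4. What the gel side removes.** Suppose 40% improve naturally on both sides, a proportion e improve through the drug, and a proportion p react by +1 on the DBI-001 side, reaction overriding improvement. The expected DBI-001 mean is p - (1 - p)[1 - 0.6(1 - e)], and the gel mean is -0.4.
- p = 10%, e = 0: 0.1 - 0.9 x 0.40 = -0.26; difference +0.14, so the reaction shows.
- p = 10%, e = 40%: 0.1 - 0.9 x 0.64 = -0.476; difference -0.076, so the average favours DBI-001.

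The gel side removes variation shared by both sides, but not a drug benefit that offsets a drug reaction on the same item.

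**5. Baseline.** Section 6.6.2 asks at baseline for the worst pain, burning or stinging in the preceding 24 hours. Asked 30 minutes after application, that window includes the first dose. A site at 0 before application, 2 at 30 minutes and 2 at Day 7 would show a change of 0.

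**The case against.** A reader might infer that tolerability cannot show harm whenever the ADSI improves. The documents do not support that.
- Section 7.3.1 plans no sum of the five items, and a single item can rise while the total falls. With erythema 1 to 2, pruritus 3 to 1, excoriation 2 to 1, and exudation and lichenification unchanged at 1 and 2, the ADSI goes from 9 to 7 while erythema shows +1.
- Pain, burning or stinging can rise in every subject without touching the ADSI.

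The plan also has safeguards outside 7.3.1.
- General Statistical Considerations promises counts and percentages for categorical parameters, and the minimum and maximum for continuous ones. If change is tabulated by category, the four sites at +2 would appear. This stands as a partial answer, but 7.3.1 does not say that the items will be treated as categorical, and counts for each side separately do not show whether the same subject worsened on one side only.
- Section 7.2.3 already compares the five components within subject, so it would be wrong to say that no paired comparison exists. It is filed as exploratory efficacy, nets as shown above and omits the sixth item. The repeated measures model for the secondary endpoints would also compare average change.
- Adverse event reporting takes in local reactions needing therapy or discontinuation (Synopsis, Safety Evaluation), increased severity of an existing condition (8.2) and clinically significant worsening (Other Required Safety Assessments). Graded rises below those thresholds may go uncounted. Section 7.3.2 summarises events by treatment group although every subject receives both articles, and its listed fields do not include side.

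Two cautions also stand. A rise may be natural variation, so not every worsened site is a reaction. And the protocol announces a separate SAP, not available for review, which may contain shift tables.

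**Conclusion.** The concern holds in limited form. Section 7.3.1 commits only to change from baseline, on five items shared with the ADSI plus one outside it. Average change can mask worsening in a minority: in most of the illustrations, 10% to 30% of subjects worsen while the mean lies between -0.40 and 0. The existing safeguards reduce the gap without supplying the number that the DBI-001 versus gel tolerability objective calls for, namely how many subjects worsened on the DBI-001 side only. The Day 1 baseline for tolerability is also undefined for the five shared items, which have two Day 1 scores, and unsuitable for the sixth.

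This is a reporting weakness that should be put right before unblinding. It does not affect the primary analysis. The size rests on assumed rates in 20 subjects; the documents give none.

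**What to change.** In 7.3.1 or the SAP, before unblinding:
- For each of the five shared items, at each visit and at the worst on-treatment visit, show a descriptive paired table of subjects who worsened by at least 1 and by at least 2 grades: DBI-001 side only, gel side only, both, neither. Give the number whose baseline grade left room for such a rise. State which visits count as on-treatment, Day 28 in particular, because section 6.5.2 labels that visit as follow-up.
- Name the Day 1 pre-application score as baseline for these five items.
- Report pain, burning or stinging as observed severity on each side, including the 30-minute score, because no pre-application score is stated.
- Give a confidence interval for the paired difference in proportions at the worst on-treatment visit only.
- Keep the change-from-baseline summaries.

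Avoid a battery of McNemar tests. Six items x (six visits + the worst visit) x two thresholds is 84 tests, in a plan without multiplicity adjustment. They would have little power: 4 versus 0 discordant subjects gives p = 2 x 0.5^4 = 0.125, and 6 versus 0 gives 2 x 0.5^6 = 0.031. A non-significant result could be misread as reassurance.

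The cost is one more set of descriptive tables with small counts. No new data are needed.

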7.3.2 Adverse Events

Subjects will be assessed for the occurrence of new and ongoing AEs. Descriptions of AEs will include the dates of onset and resolution (if resolved), maximum severity, seriousness, action taken regarding the investigational product, corrective treatment, outcome, and Investigator's assessment of causality. All reported treatment-emergent AEs (TEAEs), defined as any AE with an onset on or after the date of first investigational product application, will be summarized by treatment group, the number of subjects reporting TEAEs, system organ class, preferred term, severity, and relationship to investigational product. When summarizing TEAEs by severity or relationship to investigational product, each subject will be counted only once within a system organ class or a preferred term using the event with the greatest severity or causality, respectively, within each category. All reported serious adverse events (SAEs) will be summarized by treatment group, the number of subjects reporting SAEs, system organ class, preferred term, severity, and relationship to investigational product.

All information pertaining to AEs noted during the study will be listed by subject and will include a verbatim description of the event as reported by the Investigator, as well as the preferred term, system organ class, start date, stop date (if stopped), seriousness, severity, action taken regarding

the investigational product, corrective treatment, outcome and relationship to the investigational product. In addition, a listing of subjects who prematurely discontinue from the study due to AEs will be provided as well as a listing of subjects who reported an SAE.

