3. STUDY OBJECTIVES AND PURPOSE

The purpose of the study is to evaluate the effect of 27 daily applications of DBI-001 on the signs and symptoms of active AD, and the safety and tolerability of DBI-001 in subjects with active AD. Secondly, to see the effect of this treatment on the abundance of *S. aureus*. Thirdly to evaluate the presence or persistence of \swarrow and the impact on the overall microbiome following once daily application of DBI-001 for 4 weeks.

STUDY DESIGN AND ENDPOINTS

Description of the Study Design

This is a randomized, observer blinded, Aqueous Gel-controlled, once daily application for 27 days within-subject, bilateral comparison trial examining the effect of DBI-001 Gel vs. Aqueous Gel. Approximately 20 subjects will be enrolled. Women of childbearing potential will be tested for pregnancy with urine pregnancy test. Women who are pregnant or who have a positive pregnancy test will be excluded from the study. At each investigative site there will be two types of investigators: treating investigators and evaluating or observing investigators. The treating investigator(s), or delegate(s), will apply the treatments and be unblinded to treatment assignment.

DermBiont

The observing or evaluating investigator(s) will be blinded to treatment assignment and perform all clinical evaluations.

Subjects meeting the inclusion/exclusion criteria will be enrolled into the study. Each subject's comparable anatomically symmetrical, bilateral treatment sites will be randomly assigned to be treated with either DBI-001 or the Aqueous Gel control. Treatments will be applied in the clinic by a treating investigator, or designee. On weekdays at home, the subjects, or LAR, will apply under the supervision (by telemed) of a treating investigator, or delegate(s), and unsupervised (no telemed visit) on weekends. Clinical evaluations will be made by a blinded-to-treatment evaluating investigator who will grade the severity of signs and symptoms of AD (erythema, pruritus, exudation, excoriation and lichenification) to calculate the ADSI score and local tolerability, which will also include assessment of the severity of pain, burning, or stinging as reported by subjects. Samples for microbiology will be tested by qPCR for the presence and abundance of and *S. aureus*, 16s and/or whole genome sequencing will be used to characterize the entire microbiome.

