Each enrolled subject will be randomized to a test article kit number containing two different vials of test articles for each scheduled application. Each kit will contain vials labelled with "Right" or "Left", indicating the treatment side to apply onto. Treatment compliance will be monitored by recording all missed doses in source documentation and the CRF.

DATA ANALYSIS AND STATISTICAL CONSIDERATION.

General Statistical Considerations

All statistical processing will be performed using Statistical Analysis System (SAS®) unless otherwise stated. No interim analyses are planned. Except where noted, all statistical tests will be two-sided and will be performed at the 0.05 level of significance. P-values will be provided primarily for exploratory purposes.

Descriptive statistics will be used to provide an overview of the efficacy and safety results. For categorical parameters, the number and percentage of subjects in each category will be presented. For continuous parameters, descriptive statistics will include the number of subjects, mean, and standard deviation, median, minimum, and maximum. Appropriate inferential statistics will be used for the primary and secondary efficacy variables in an exploratory manner.

Linear interpolation of efficacy variables will be performed using observed data that precedes and follows the off-schedule visit, if present. The last observation will be carried forward if all the data subsequent to the off-schedule value is missing.

No adjustments will be made for multiplicity.

DermBiont

The number of subjects in each analysis set will be summarized. Reasons for study withdrawal will be summarized using frequencies and percentages by treatment group.

Reported AEs, medical history terms and prior and concomitant procedures and therapies will be classified on the basis of the f Medical Dictionary for Regulatory Activities (MedDRA) terminology. Prior and concomitant medications will be classified on the basis of the World Health Organization Drug Dictionary (WHO-DDE) terminology.

A statistical analysis plan (SAP), describing all statistical analyses will be provided as a separate document. The SAP will be finalized prior to unblinding of the study treatments.

Analysis of Efficacy Data for Objectives

7.2.1 Primary Efficacy:

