7.5 Sample Size Determination

Sample size is based on clinical judgement and deemed adequate to successfully demonstrate these goals.

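### AE, SAE and withdrawal tables are planned by treatment group, but every subject receives both products and the plan does not require an AE's side to be recorded

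*Combined protocol and SAP*

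**What the plan says.** **Design.** Description of the Study Design states: "Each subject's comparable anatomically symmetrical, bilateral treatment sites will be randomly assigned to be treated with either DBI-001 or the Aqueous Gel control". Under Randomization, each subject is "randomized to a test article kit number containing two different vials of test articles for each scheduled application", with vials marked for the right or left side. On size: "Approximately 20 subjects will be enrolled".

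**AE tables.** Section 7.3.2, repeated in the synopsis under Analysis of Safety, says TEAEs "will be summarized by treatment group, the number of subjects reporting TEAEs, system organ class, preferred term, severity, and relationship to investigational product". SAEs are laid out the same way. Where TEAEs are broken down by severity or relationship, "each subject will be counted only once within a system organ class or a preferred term", keeping the worst grade. That counting rule is stated for those TEAE breakdowns only.

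**Withdrawals.** General Statistical Considerations: "Reasons for study withdrawal will be summarized using frequencies and percentages by treatment group".

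**AE items.** Section 7.3.2 names dates, severity, seriousness, action taken, corrective treatment, outcome and causality; the listing adds the verbatim and coded terms. Side or treated site is not among them.

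**Local tolerability.** This is handled separately. Section 4.2.2 and the synopsis compare the scores between the DBI-001 lesion and the Aqueous Gel lesion.

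**The concern.** The AE and withdrawal text is written as for a parallel-group trial. Here both columns of a by-treatment table hold the same people, and nothing says which column takes an event that belongs to the person rather than to a site.

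Comparing the safety of DBI-001 with Aqueous Gel is a stated secondary objective. Local AEs are also foreseeable: the synopsis (Safety Evaluation) makes a local reaction an AE once it needs concomitant therapy or leads to discontinuation, and Potential Risks names worsening AD, impetigo, folliculitis and cellulitis. The tolerability scores cover five AD signs and symptoms plus pain, burning or stinging, so they do not record the three infections as such. For those, a side-specific AE table is the natural comparison, and it depends on knowing the side.

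**Working it through.** The plan gives no safety figure to reproduce. The only relevant number is about 20 subjects, for which section 7.5 offers "Sample size is based on clinical judgement and deemed adequate to successfully demonstrate these goals". All event counts and rates below are assumptions for illustration.

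**Step 1. Which events have a product?**

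| Event | Can it belong to one product? | Rule in the plan |
|---|---|---|
| Application-site AE, one side | Yes, if the side is recorded | No side required |
| Application-site AE, both sides | Both, once per site | Counting level not stated |
| Non-site AE | No | By treatment group |
| SAE not tied to a site | No | By treatment group |
| Withdrawal of the subject | No (section 6.4.1 concerns subjects, not sites) | By treatment group |

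**Step 2. Non-site events duplicated in both columns.** Let S be subjects with a non-site TEAE, a those with a local TEAE on the DBI-001 side only, and b those with one on the gel side only, all distinct, with n = 20. The any-TEAE row shows (S + a)/n versus (S + b)/n. The difference is (a − b)/n, free of S. The ratio (S + a)/(S + b) moves towards 1 as S grows.

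With S = 4, a = 3, b = 1:
- Duplicated: 7/20 = 35% versus 5/20 = 25%; difference 10 points, ratio 7/5 = 1.4.
- By site: 3/20 = 15% versus 1/20 = 5%; difference 10 points, ratio 3/1 = 3.0.

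So duplication weakens the relative contrast and leaves the absolute one unchanged, provided the subjects are distinct. If one of the three DBI-001-only reactors is also one of the four with a non-site AE, that person already counts in both columns: 6/20 = 30% versus 5/20 = 25%, and the difference falls to 5 points. Rows for application-site preferred terms are not affected by non-site events.

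**Step 3. Non-site events placed in one column.** Each such event in a subject not otherwise counted there moves the difference by 1/20 = 5 points, towards whichever column was chosen. The plan gives no basis for choosing.

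**Step 4. The once-only rule.** Applied within each treated site, it loses nothing between sides. Applied across sides, a term that is mild on one side and severe on the other survives only as severe, and the milder side's event disappears. With the same rate p at each site, the expected number of subjects with the term on both sides is 20p² if the sides are independent and at most 20p if they always agree:

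| p | Independent, 20p² | Full agreement, 20p | Site events, 40p |
|---|---|---|---|
| 10% | 0.2 | 2 | 4 |
| 20% | 0.8 | 4 | 8 |
| 30% | 1.8 | 6 | 12 |

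Under independence the loss is at most 1.8/12 = 15% of site events. Both sites share one patient and the same swabbing, so positive correlation is plausible and the loss could be larger. It falls on the milder side of each pair, which may be either product.

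**The case against.** The case for leaving the plan alone has real substance.

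- *Tolerability is already compared by site.* Both lesions are scored by a blinded evaluator 30 minutes after application at Baseline and at each later visit, and the comparison by treated lesion is a secondary endpoint. This stands, and it confines the point to the AE, SAE and withdrawal tables. A reader might infer that the trial cannot compare the products on safety at all; the documents do not support that.
- *The once-only rule may be harmless.* A reader might infer that it deletes one side of every bilateral reaction, or that it also governs SAEs and withdrawals. Neither follows. It is limited to TEAEs by severity or relationship, and counting once within each treatment column is an ordinary reading. What remains is that the level is not stated.
- *The side may be recorded anyway.* The list of AE items need not be exhaustive, the verbatim term may mention the side, and the CRF is not among the documents. Since vials are marked right or left, a recorded side identifies the product. This stands as far as it goes: absence from the CRF is not established. But nothing requires the side, and the relationship scale in section 8.5 grades causality without saying which site reacted.
- *Consequences are limited.* AE reporting is descriptive, full listings by subject are planned for about 20 subjects, and a separate SAP is promised before unblinding. An SAP can set table conventions, but it cannot reliably recover a side that was never collected.

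**Conclusion.** The point holds for the AE, SAE and withdrawal tables. Tabulating by treatment group cannot be carried out for non-site AEs, SAEs not tied to a site, or withdrawals of subjects without duplicating or arbitrarily placing them. For local AEs, attribution to a product depends on a side that the plan does not require. This rests on the text of the design and section 7.3.2, not on any assumed count.

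The size is modest and depends on assumptions. In the example, duplication takes the any-TEAE ratio from 3.0 to 1.4 while the difference stays at 10 points. The loss from the once-only rule arises only if it is applied across sides, and is small if the sides are independent.

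A reader might also infer that the finished tables will be wrong in either direction. That is not shown: the plan states no placement rule, and under duplication with distinct subjects the absolute contrast is preserved. The change is worth making because the gap touches a stated objective and is cheap to close, but only reliably so while the side can still be recorded.

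**What to change.** 1. Require each AE record to state right site, left site, both, or not site-specific. Where both sites are involved, record severity and relationship for each.
2. Tabulate application-site TEAEs by treated site, apply the once-only rule within each site, and show the number of subjects with the event on the DBI-001 site only, the Aqueous Gel site only, and both. Any comparison should be paired.
3. Report all other TEAEs, SAEs and withdrawal reasons once, in a single overall column. An SAE that is an application-site event can also appear in the site table.
4. Amend section 7.3.2, the matching synopsis text and the withdrawal sentence in General Statistical Considerations, and carry the same rules into the SAP.

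Cost: one AE field, if the CRF does not already hold it, and revised table shells. No added visits or subjects.
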